### 13.3. Adverse Event Documentation and Reporting Procedures

#### 13.3.1. Procedures to Document AEs

Study participants will be instructed to contact medical monitor if any serious or unexpected adverse event occurs. Study staff will inquire about AEs when treatment is administered and during the follow-up phone calls following the patients discharge. AE's will be recorded and documented in detail in an AE CRF.

AE information to be collected in the AE CRF:

- Nature of the event
- Date of onset
- Concomitant treatment: product (generic name), indication, dosage, dosage interval, presentation, mode of administration, administration regimen
- Duration of the AE
- Severity
- Seriousness
- Causality
- Outcome

The course and outcome of the adverse event will be commented on as follows:

- Recovered without sequelae
- Not yet recovered
- Recovered with sequelae
- Fatal

#### 13.3.2. Procedures to Report AEs

Any SAE (including death, irrespective of the cause) occurring during the study will be immediately reviewed by the PI/medical monitor, the DMC, and the Health Sciences IRB (the IRB of record for this study).

If determined to be a SUSAR (suspected unexpected serious adverse reaction – SUSAR; Appendix II) by the PI/medical monitor, the event will be reviewed by the DMC. Regulatory filing to the FDA or local

IRB as per standard practices will occur. Any hospital related death due to a bowel obstruction or infection that could be related to FMT will be reviewed by the DMC to discuss a temporary suspension of the protocol until a full safety review is conducted.

In case of a SAE (non-SUSAR), the site PI will report the event to the study medical monitor and lead PI for review and compilation. The DMC will review all SAEs every 6 months or *ad hoc* depending on the clinical case at the discretion of the PI/medical monitor. A specific SAE CRF will be provided similar to Appendix 17.3. The report must contain a detailed description of the symptoms observed and the concomitant treatment administered. Furthermore, the report must comment on a possible causative relationship between the AE and the trial medication. Each SAE must be followed until it is resolved or can be explained satisfactorily.

For non-serious adverse reactions (definitely related, not related) the medical monitor/PI will complete a report. All non-serious adverse reactions will be reviewed by the DMC every 6 months or *ad hoc* depending on the clinical case at the discretion of the PI/medical monitor.

In accordance with safety requirements, the PI will inform the local IRB and will make sure that the involved persons will obtain adequate information. The following instructions must be heeded:

- In the case of an intolerable SAE, the study patient must, at the decision of the PI, be withdrawn from further treatment/placebo, and symptomatic treatment must be administered. The participant may opt to voluntarily provide samples for duration of study.
- The measures taken must be recorded on the CRF.
- In accordance with local legislation, the PI will submit copies of the final SAE-report to the Regulatory Authorities concerned, if necessary.

### **13.4. Follow-up after Adverse Events**

AEs will be followed until resolution or stability even if this extends beyond the study-reporting period. Resolution of an AE is defined as the return to pretreatment status or stabilization of the condition with the expectation that it will remain chronic.

Follow-up procedures, evaluations, and outcomes will be recorded on the participant's case report forms.

### **13.5. Study Halting Rules**

#### **13.5.1. *Study Halting Rules***

Enrollment and administration of study intervention will be suspended pending a safety review by the DSMB to determine whether the study will be terminated or re-initiated in the following situations:

- Three or more of the randomized participants in a study treatment group have a Grade 3 AE of the same organ system deemed related to the study intervention.
- Any serious adverse event of an enrolled participant related to the study intervention including transmission of a pathogen from donor to recipient.
- An overall pattern of symptomatic, clinical, or laboratory events that the Medical Monitor considers related to study product and that may appear minor in terms of individual events, but that may collectively represent a serious potential concern for safety.

The FDA and AHRQ will be notified of any study halt that occurs as a result of any of the above halting criteria.

### **13.5.2. *Individual's Halting Rights***

Participants who meet any of the following criteria must be assessed by the site PI to determine if it is in the participant's best interest to stop the study product(s):

- Participant choice (withdrawal of consent).
- Participant's non-compliance.
- Development of a significant medical condition and/or participation in the study is no longer in the best interest of the participant.
- Development of a severe or serious AE related to the FMT product.

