patient's antibiotic treatment plus seven days post-antibiotic treatment.

**Group 2:** This group will receive 30 oral FMT capsules one time 48-72 hours following completion of antibiotic treatment.

**Oral FMT capsules:** Capsules contain fecal microbiota sourced from healthy donors and screened for pathogens.

**Control:** The control is an oral placebo capsule identical to the FMT capsules given to the intervention groups and will be provided by OpenBiome. The placebo capsule consists of glycerol and saline and will be administered daily as five capsules per day during the duration of antibiotic treatment plus an additional seven days post-antibiotic treatment (group 3). Patients will be fasting (clear liquids allowed) for at least 2 hours prior to administration and at a minimum of 1-hr post-administration (Appendix 17.1)

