### **8.3. Exclusion Criteria**

1. Admitted to an intensive care unit (ICU).
2. Females who are pregnant, lactating, or planning to become pregnant during the study. Female patients of childbearing potential will take a pregnancy test at the intervention visit and will be excluded if pregnant.
3. Inability (e.g. dysphagia) to or unwilling to swallow capsules.
4. Known or suspected toxic megacolon and/or known small bowel ileus.
5. Bowel obstruction or other gut motility issues occurring in the last two weeks that are unresolved as noted by the patient or in the EMR.
6. Major gastrointestinal surgery (e.g. significant bowel resection) within 3 months before enrollment not including appendectomy or cholecystectomy.
7. History of bariatric or colectomy surgery.

8. Concurrent intensive induction chemotherapy, radiation therapy, or biologic treatment for an active malignancy. Patients on maintenance chemotherapy may be enrolled after consultation with the medical monitor.
9. Expected life expectancy <6 months.
10. Patients with severe anaphylactic or anaphylactoid food allergy.
11. Solid organ transplant recipients ≤90 days post-transplant or on active treatment for rejection.
12. Neutropenia ( $\leq 500$  neutrophils/mL) or other severe immunosuppression. Anti-TNF will be permitted. Patients on monoclonal antibodies to B and T cells, glucocorticoids, antimetabolites (azathioprine, 6-mercaptopurine, methotrexate), calcineurin inhibitors (tacrolimus, cyclosporine), and mycophenolate mofetil may only be enrolled after consultation with the medical monitor.\*
13. At risk of CMV/EBV associated disease, negative IgG testing for cytomegalovirus (CMV) or Epstein Barr Virus (EBV).
14. Any other gastrointestinal illness including diarrhea.
15. On oral vancomycin or metronidazole.
16. Having been taking the currently prescribed antibiotic for over 72 hours.
17. On an antibiotic treatment anticipated to exceed 19 days.
18. Having received an FMT by any route in the 90 days prior to enrollment.
19. Any condition that would jeopardize the safety or rights of the patient, would make it unlikely for the patient to complete the study, or would confound the results of the study.

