## **8.4. Subject Screening and Retention**

### ***8.4.1. Subject Identification***

Potential subjects will be identified by the study team who has access to a list of patients admitted to UWHC for infectious diseases that is updated daily. The medical monitor will screen these patients' EMR to determine eligibility. Once potential subjects meeting the eligibility criteria are identified, the treatment team's physician or nurse will ask the patient if he/she is interested in hearing about the study and if so, will introduce the research team. The patient will be invited to hear about the study and, if interested and meeting all eligibility criteria, participate in the study. As patients with community acquired pneumonia (CAP) and urinary tract infections (UTIs) are likely to be on shorter antibiotic courses, initial recruitment will focus on these patients. We, however, do not plan to limit to just CAP and UTI patients and will consider patients admitted to other non-ICU acute care units or outpatients with anticipated short courses (2 weeks or fewer) of antibiotic treatment.

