#### **8.4.2.2. *Retention***

Stool samples will be taken from all subjects at baseline and every 3 days  $\pm$  1 day regardless of treatment group while the patient is hospitalized. If/when a patient is discharged from the hospital, the patient will continue to provide stool samples every three days during FMT and once weekly for 4 weeks following FMT. We will call or email the patient weekly until they have completed FMT and once weekly during follow-up to remind him/her to mail us a stool sample and discuss the patient diary. If the patient is receiving either the daily FMT or placebo, we will also remind him/her to be taking his/her capsules as well as ask him/her to count how many pills he/she currently has left for us. If a patient in the one-time FMT group is discharged prior to the FMT consumption time point (48-72 hours post antibiotic treatment completion), he/she will be asked to return to the ID clinic or CRU to receive his/her FMT capsules. Inpatients in the daily and placebo groups will have each dose of 5 capsules observed by a nurse/physician during admission and will be discharged with a cooler containing their FMT capsules and instructed on use. Outpatients in the daily and placebo groups will be asked to come to the ID clinic or CRU to have their first dose observed by a nurse or physician and be given the remaining FMT doses to take home. After discharge, all patients will receive a study brochure tailored to their study arm describing all post-discharge study procedures.

While we will target patients who are on antibiotic doses with a duration of less than 14 days, if a patient's antibiotic regimen exceeds 14 days will be handled in the following manner:

Group 1: Patients will be given the 30 capsule dose of FMT on day 16 or 17 (day 14 + 48 to 72 hours) of antibiotic treatment unless they meet one of the criteria for halting a patient's participation in the study (13.5.2). Participants who are not withdrawn from the study will continue follow-up the same as other patients.

Groups 2 and 3: At 14 days of antibiotics, we will discontinue the daily FMT treatments and patients will move to the weekly follow-up phase of the study unless they meet one of the criteria in section 13.5.2 in which case they will be withdrawn from the study.

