##### **8.6.2.1. *Data Collection and Follow-up for Withdrawn Subjects***

If the subject is willing, the coordinator will ask to schedule a close-out study visit to collect a final stool sample and follow-up safety evaluation.

A subject may withdraw from the study at any time for any reason with no consequences. A participant

may be withdrawn from the study by the Investigator for the following reasons:

- Adverse event that may make it no longer in the best interest of the subject to continue to participate
- Recurrent *C.diff* infection
- Participant's choice
- Protocol violation/ non-compliance
- Pregnancy
- Lost to follow-up
- Other (must be noted)

The primary reason for withdrawal from the study will be recorded. Participants will be encouraged to complete the Early Termination Visit. The Early Termination Visit procedures are listed in Section 11.4. Although participants are free to withdraw at any time, subjects will be encouraged to remain in the study for follow-up safety evaluation. Every attempt should be made to follow all AEs and SAEs ongoing at the time of early withdrawal to resolution or until stabilized. If possible, a final stool sample will be collected at the time of Early Termination. All subjects who are randomized will be included in the safety analysis.

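### Two withdrawal rules can end stool sampling for reasons that justify only stopping study product

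*Combined protocol and SAP*

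**What the plan says.** **Stopping product.** Section 13.5.2 asks the site PI to assess certain patients "to determine if it is in the participant's best interest to stop the study product(s". Its criteria are withdrawal of consent, non-compliance, a significant medical condition or participation no longer being in the patient's interest, and a severe or serious adverse event related to the product. It does not mention later stools.

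**Courses beyond 14 days.** Section 8.4.2.2 has a branch that begins "Groups 2 and 3: At 14 days of antibiotics, we will discontinue the daily FMT treatments". These patients move to weekly follow-up "unless they meet one of the criteria in section 13.5.2 in which case they will be withdrawn from the study". The companion branch gives the 30-capsule dose "unless they meet one of the criteria for halting a patient's participation in the study (13.5.2". It labels its patients Group 1, but in 7.1 the single-dose arm is Group 2: "This group will receive 30 oral FMT capsules one time 48-72 hours following completion of antibiotic treatment". The two labels in 8.4.2.2 therefore appear to be swapped, and the branch that discontinues daily treatment appears to mean the daily arms, Groups 1 and 3.

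**Investigator withdrawal.** Under 8.6.2.1 a participant "may be withdrawn from the study by the Investigator for the following reasons". The list includes protocol violation or non-compliance. It also includes an adverse event, but only one that may make continued participation contrary to the patient's best interest.

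**Consequence.** Section 11.4 stops study procedures at early termination. What remains is a clinical and data assessment, attempts to collect the diary and a final stool, and, with permission, passive follow-up through the medical record.

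**Outcome and analysis.** Section 7.2.1 defines the primary outcome on stools taken at baseline, every 3 days, and weekly for a month after the intervention. Section 9.8 calls for intention-to-treat analysis. Section 12.2 plans for 8 of 10 patients per group to complete treatment and be analyzed.

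**The concern.** Stopping a product and leaving a study are different events, and an intention-to-treat analysis depends on keeping them apart. Section 13.5.2 is framed as a decision about product, but 8.4.2.2 treats meeting one of its criteria as grounds for leaving the study. In the day-14 branch daily product ends for everyone, so withdrawing the patient spares no dose. Its practical effect is to end sampling.

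The stools at stake belong to the primary outcome. The patients who lose them are selected by poor adherence or illness, both of which may be related to the state of the gut microbiota. Opportunity for dosing non-compliance also differs by arm. Groups 1 and 3 may take capsules at home for days or weeks, while Group 2 takes one observed dose. Loss for this reason could therefore fall unevenly between single-dose FMT and placebo.

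**Working it through.** The plan derives its sample size from patient availability, so there is no power figure to reproduce. The stated total checks: 3 × 10 = 30.

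**What each section does with an off-product patient**

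| Section | Effect |
|---|---|
| 11.2, all subjects | 3-day stools until the intervention is complete, then weekly for a month; no clause on early stopping |
| 11.2, Groups 1 and 3 | Foresees missed doses, but only for capsule return |
| 9.8 | Records the dose taken; names intention-to-treat; silent on sampling |
| 13.3.2 | After an intolerable SAE, off treatment; samples voluntary |
| 8.4.2.2, default | Daily product stops at antibiotic day 14; weekly stools continue |
| 8.4.2.2, with a 13.5.2 criterion | Mandatory study withdrawal |
| 8.6.2.1 | Discretionary study withdrawal for non-compliance |

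The first five rows keep the patient in, or lean that way. The last two can take the patient out.

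**Stools lost per withdrawn patient**

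Inputs: 3-day stools on study days 0, 3, 6 and so on up to the last product day, then 4 weekly stools (section 3 and 11.2). Enrollment comes within 72 hours of starting the antibiotic (8.2), so antibiotic day 14 falls on study day 11 to 14. Study days 7 and 10 for a discretionary withdrawal are assumed examples.

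Share lost = 4 / (3-day stools obtained + 4). If the final stool is obtained, the numerator is 3.

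| Case | 3-day stools obtained | Share lost | Net of final stool |
|---|---|---|---|
| Day-14 rule, study day 11 | 4 (days 0, 3, 6, 9) | 4/8 = 50% | 3/8 = 38% |
| Day-14 rule, study days 12–14 | 5 (adds day 12) | 4/9 = 44% | 3/9 = 33% |
| Discretionary, study day 10 | 4 | 4/8 = 50% | 3/8 = 38% |
| Discretionary, study day 7 | 3 (days 0, 3, 6) | 4/7 = 57% | 3/7 = 43% |

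For discretionary withdrawal these counts leave out any 3-day stools between withdrawal and the planned end of treatment.

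**Per arm.** Planned weekly stools: 10 × 4 = 40. One such patient is 4/40 = 10%. Once the 2 losses per arm that the plan allows (10 − 8) are used up, one more is 4/(8 × 4) = 4/32 = 12.5%. With 1, 2 or 3 such patients in an arm, 36, 32 or 28 of the 40 remain. The plan gives no rate from which to choose among these.

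**Timing of retained stools.** Assume a 14-day course with daily product to about study day 21. The planned weekly stools fall at about days 28, 35, 42 and 49. If a patient who stops on day 7 went straight to weekly sampling, they would fall at about days 14, 21, 28 and 35, the first around the end of antibiotics. A fix must therefore count from the planned end of treatment, not from the stop date.

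**The case against.** The strongest reply is that the protocol's default already keeps these patients in. Section 11.2 puts all subjects on weekly stools once treatment has concluded, and an early stop can be read as a conclusion. Sections 9.8 and 13.3.2 separate product decisions from participation, and 11.4 can be read as preferring active follow-up where it is viable. This largely stands. A reader might infer that the protocol drops anyone who stops or misses product, and the text does not support that. But a favorable default does not override two written rules that say otherwise.

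A reader might also infer that any adverse event permits withdrawal under 8.6.2.1. It does not: the item requires that continued participation may be against the patient's interest, and that is a proper exit.

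The mandatory rule is narrow. Recruitment looks for "anticipated short courses (2 weeks or fewer) of antibiotic treatment", and the rule needs a 13.5.2 criterion as well. Two of those criteria, withdrawal of consent and participation against the patient's interest, are legitimate reasons to leave. The narrowness stands, although the exclusion reads "On an antibiotic treatment anticipated to exceed 19 days", so expected courses of 15 to 19 days are admissible.

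Finally, 12.2 speaks of analyzing patients who complete treatment, so retained stools might not enter the analysis. This stands as well, and the fix must cover 12.2.

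**Conclusion.** The point holds in limited form. Section 8.4.2.2 makes study withdrawal mandatory, and 8.6.2.1 makes it possible, for reasons such as non-compliance that justify only stopping product. Each affected patient loses up to 4 weekly primary-outcome stools, 3 net if the final stool is obtained. That is 33–57% of the patient's series in the cases shown, taking 3-day sampling to end with product and using assumed stop days for the discretionary rule.

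The percentages are per affected patient, not effects on the trial. A reader might infer that the primary analysis is invalidated. The documents do not support this: one rule is narrow, the other is discretionary, no frequency is given, and the trial is a pilot. Stools already collected and the safety analysis are kept. Enrolling 10 for 8 allows for some loss, and the linear mixed models in section 2 can use incomplete series under an assumption about why stools are missing. The extra enrollment covers the number lost, but not the selection by adherence or illness. The change is worth making because it is cheap. Confidence is medium.

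**What to change.** - **8.4.2.2:** Except for withdrawal of consent, or where continued participation is against the patient's interest, replace mandatory withdrawal with no further product and entry into weekly follow-up. Correct the labels to match 7.1: Group 2 for the 30-capsule branch, Groups 1 and 3 for the daily branch.
- **8.6.2.1:** Make dosing non-compliance a reason to stop product, not to leave the study. Leave the adverse-event item as it is.
- **11.4 and 13.5.2:** State that stopping or missing product alone does not end participation. Such patients keep 3-day sampling to the originally planned end of treatment where feasible, then give the 4 weekly stools, so that time points stay aligned with other patients. For a single-dose patient who never takes the dose, count from the planned dose date.
- **12.2:** Analyze randomized patients with stool data whether or not they completed treatment, in line with 9.8.

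The cost is wording in five sections and a few more mailed stools and calls per affected patient. Some patients will decline, so part of the loss will remain.

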### **13.6. Safety Oversight – Data Monitoring Committee (DMC)**

UW-ICTR has established a Data Monitoring Committee (DMC) to provide a key resource for UW-Madison investigators conducting clinical research. This DMC will provide investigators services to ensure appropriate measures are in place to promote subject safety, research integrity and compliance with federal regulations and local policies for individual clinical research protocols in need of DMC review (as determined by the Principal Investigator (PI), the funding agency, the local Scientific Review Committee, or the local IRB, and for which no DMC exists). For these studies, the UW ICTR DMC will be the primary data and safety advisory group for the Principal Investigator.

The DMC is supported in its mission of safety and compliance by experienced ICTR staff to provide administrative assistance, experienced members representing a diversity of backgrounds, skills and knowledge, and the use of the Research Electronic Data Capture (REDCap) tool which provides data management functionality by allowing the development of eCRFs and surveys to support data capture. In providing oversight for the conduct of this study, the ICTR DMC will meet every 6 months during the 1-year study. Additional meetings may be scheduled as determined by the DMC or as requested by the PI. The DMC members will review protocol-specific reports created by statisticians that serve a non-voting member role on the DMC using data pulled from REDCap. These standard reports will include an overview of study objectives, a review of actual and projected accrual rates, an evaluation of patient demographics for balance of randomization, and a summary of the number and seriousness of adverse events. An interim analysis of study results may be performed and source documents may be reviewed to allow the DMC to independently judge whether the overall integrity and conduct of the protocol remain acceptable based on data provided and reported by the Principal Investigator. Additionally, the DMC may conduct a safety interim analysis after 50% of patients have enrolled in the daily treatment arm. The DMC will make recommendations to the Principal Investigator that could include actions of continuation, modification, suspension, or termination.

